14.2 Efficacy

Primary: The primary efficacy outcome is increase in the count of total, motile sperm after twenty-four weeks of study treatment.

Secondary: The magnitude and changes between baseline and week 24 in terms of total, motile sperm count will be described for subjects in each treatment arm.

14.3 Safety

Laboratory data, physical examination results, vital signs and chemistry levels will be assessed and compared for each subject from screening to end of study. All adverse events will be recorded and coded using the body system coding of MedDRA.

The incidence of adverse events will be examined by dose and where appropriate for trend by subject, clinic and time, using descriptive statistics. Clinical chemistries and allied data will be examined for change over time.

15. Adverse Events

Adverse Events (AE) should be carefully monitored and an AE form is included in the CRF. Serious adverse events (SAE) as defined below will have to be reported on the SAE form included as an appendix.

All adverse experiences must be recorded in the study event record of the subject's CRF, and must include the following information (when applicable):

- Specific condition or event
- Indication of whether the condition was pre-existing or not and if yes, whether it has worsened in severity (including an increase in frequency)
- Date of occurrence
- Date of resolution
- Relationship to study medication as evaluated by the investigator (causality assessment). The investigator must enter their opinion of causality on the AE forms.
- Action taken (study medication continued or not) and outcome
- Seriousness according to the approved regulatory classification {i.e. any event that is fatal, life-threatening, disabling, incapacitating, results in or prolongs hospitalization, or is a medically significant event, e.g. an intervention to prevent one of the above outcomes, or any other serious criteria (cancer, congenital anomaly, overdose, other significant) is considered serious}.

When any serious adverse drug experience, regardless of causality, is encountered during this clinical trial at an investigator's site, the investigator must notify the Study Monitor by facsimile using the form provided as an appendix. This report must be submitted within 2 calendar days from the time the investigator's staff is notified of the event.

All serious adverse events that are unexpected will be reported to the FDA by the principal investigator or his designated surrogate. All serious adverse events will be followed until fully characterized. The investigator will collect and forward to the FDA via fax, all available supporting documentation (with subject name redacted) for serious events, including at a minimum hospital discharge summaries and death certificates (where applicable). Additional supporting documentation that should be collected whenever possible, to verify the medical diagnosis, includes autopsy reports (where applicable), surgical procedure summaries, histology reports, and imaging reports.

16. Ethical Considerations

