Criteria	Klinefelter syndrome or Y-chromosome microdeletions), hypogonadotropic hypogonadism (that might respond to gonadotropin injections), the use of anabolic steroids, illicit drugs, or the consumption of more than 4 alcoholic beverages daily, severe mental health problems, or current therapy with retinoic acid (e.g. Accutane) or vitamin A.

Efficacy	In this study, count of total, motile sperm after 24 weeks of
Parameters	treatment.
Safety	CBC, clinical chemistry panel (glucose, liver and renal
Parameters	function tests including urea, creatinine, albumin, alanine aminotransferase, aspartate aminotransferase, alkaline phosphatase, bilirubin), full lipid panel including Total cholesterol, HDL, LDL, triglycerides at screening and at the end of treatment. Additional measures will be conducted if any abnormal values are found until the end of study visit. • Adverse event and concomitant medications throughout the study. Other safety parameters include vital signs; and changes in pre- and post-treatment physical examination results and score on the PHQ9 depression questionnaire.
Evaluations	The following determinations will be made in all subjects: • Serum samples will be collected for the measurement of concentrations of vitamin A, all-trans and 13-cis retinoic acid, testosterone, FSH and LH will be collected before the beginning of the treatment, and monthly during treatment.
Other Assessments	Demographic characteristics, including age and race, will be collected
Statistical	The primary endpoint is the effect of treatment on the count
	of total, motile sperm between treatment groups after 24
Analysis	weeks. This analysis will be conducted using a Kruskal-Wallis ANOVA is the primary endpoint.

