This data suggests that lower intratesticular retinoic acid is associated with impaired spermatogenesis; however, it is unclear from this cross-sectional data if the low retinoic acid is a result of the infertility or a cause of it. Only an interventional trial of retinoic acid in infertile men will answer the question of the ability of retinoic acid to improve spermatogenesis in this population.

Objectives

2.1 Primary Objective:

To determine the effect of 13-cis retinoic acid administration on total motile sperm count in men with oligoasthenoteratozoospermia

2.2 Secondary Objectives:

- o To determine the chance of pregnancy during treatment with 13-cis retinoic acid
- o To determine the concentration of 13-cis retinoic acid in the seminal plasma of treated men
- o To determine the side effects and tolerability of treatment with 13-cis retinoic acid

3. Rationale, Benefits and Risks

Male infertility is common and difficult to treat unless men have an easily identified gonadotropin deficiency. Many men have idiopathic infertility. Retinoids are necessary for spermatogenesis, but no controlled studies of retinoic acid administration to men with infertility have been conducted. We have shown that men with abnormal spermatogenesis have lower than normal levels of intratesticular retinoic acid, suggesting that intratesticular retinoic acid deficiency is associated with infertility. In this study, we aim to determine if retinoic acid therapy can improve sperm counts in men with low sperm counts. The medication, 13-cis retinoic acid is widely available and prescribed for the treatment of acne, suggesting that serious adverse events, especially at the low doses to be tested are unlikely.

4. Compliance

All aspects of this study will be performed according to GCP and ICH guidelines, under an active IND.

5. Study Design

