9.2 Exclusion Criteria

Men who meet any of the following criteria are NOT eligible for enrollment in the trial:

- 1. Men participating in another clinical trial
- 2. Men not living in the catchment area of the clinic
- 3. Clinically significant abnormal findings at screening
- 4. Known genetic infertility (e.g. Klinefelter syndrome or Y-chromosome microdeletions),
- 5. Hypogonadotropic hypogonadism (that might respond to gonadotropin injections),
- 6. The use of anabolic steroids, illicit drugs, or the consumption of more than 4 alcoholic beverages daily
- 7. Severe mental health problems requiring medications
- 8. Current therapy with retinoic acid (e.g. Accutane) or vitamin A.
 - 9. Abnormal serum chemistry values according to local laboratory normal values, which indicate liver or kidney dysfunction. Other abnormal lab values may also be exclusionary, at the discretion of the investigator

10. Concomitant Treatment

Concomitant medications that are exclusionary include:

- Use of sex hormones for treatment
- Use of androgens or other compounds for body building
- Use of retin-A or Accutane for the treatment of acne

Concomitant medications are discouraged except as prescribed for the treatment of intercurrent medical conditions. All concomitant treatments will be recorded on the subject's case record form (CRF), including the generic name of the drug, start and stop dates, and reason for use.

11. Study Materials

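### As written, section 14.3 analyses laboratory, vital-sign and examination data as change within each man, without using the placebo arm, and leaves out PHQ-9

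*Combined protocol and SAP*

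**What the plan says.** Section 14.3 (Safety) gives three instructions.

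- Laboratory, examination and vital-sign data: "Laboratory data, physical examination results, vital signs and chemistry levels will be assessed and compared for each subject from screening to end of study".
- Chemistries: "Clinical chemistries and allied data will be examined for change over time".
- Adverse events: "The incidence of adverse events will be examined by dose", using descriptive statistics.

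Only the third refers to treatment. The synopsis, under Safety Parameters, also lists "changes in pre- and post-treatment physical examination results and score on the PHQ9 depression questionnaire". That is a before-and-after description, and 14.3 does not take up the PHQ-9 at all.

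Elsewhere, section 2.2 makes side effects a secondary objective: "To determine the side effects and tolerability of treatment with 13-cis retinoic acid". Section 5 describes a randomized, double-blinded trial with a placebo arm. The three-group test in section 14 covers total motile sperm only. Exclusion 9 in section 9.2 removes men with "Abnormal serum chemistry values according to local laboratory normal values, which indicate liver or kidney dysfunction"; other abnormal laboratory values may exclude at the investigator's discretion.

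**The concern.** A before-and-after change in one man, or in one arm, combines any drug effect with assay drift, season, ageing of the cohort and chance. The concurrent placebo arm exists to remove those shared components. Section 14.3 uses the arms for adverse events but not for the measured safety data.

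At stake is how part of a stated secondary objective is read. If some men on active drug move above a laboratory limit, or an arm's mean lipid value or PHQ-9 score rises, the written analysis gives no yardstick for what would have happened without drug. A by-arm comparison chosen only after unblinding would leave open which tests, visits and thresholds to report.

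**Working it through.** **The plan's own figure.** There is none for safety. The only sample-size statement (section 14.1) concerns sperm count. It is used here only for the 10% drop-out: 20 × 0.9 = 18 evaluable men per arm.

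**Inputs from the documents.** 20 men per arm (section 7). Six on-treatment visits, weeks 4 to 24 (section 12.4, Appendix 1). Fifteen named chemistry, lipid and hematology tests (section 12.4.2).

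**Assumptions.** The documents give no laboratory SDs or abnormality rates. I take values as normally distributed, 8 to 12 tests for which a high value matters, an upper limit at the 97.5th percentile, all tests below it at screening, equal correlation between visits within a man, and no drug effect.

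*1. Chance new high values.* By simulation, a man below the limit at screening exceeds it at one or more of six later visits with probability p = 0.042 (within-man correlation 0.85) to 0.092 (correlation 0.5) per test. For k independent tests, P(at least one) = 1 − (1 − p)^k:

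- k = 8: 1 − 0.958^8 = 0.29, and 1 − 0.908^8 = 0.54
- k = 12: 1 − 0.958^12 = 0.40, and 1 − 0.908^12 = 0.69

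Related tests (the two aminotransferases, total and LDL cholesterol, hematocrit and hemoglobin) are not independent, so I repeated the simulation with between-test correlation of 0.3 to 0.5. I also repeated it with one post-screening value, because the synopsis places chemistry at screening and end of treatment only.

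| Post-screening values | Tests independent | Between-test correlation 0.3–0.5 |
|---|---|---|
| Six | 29–69% of men | 17–52% |
| One | about 10–23% | about 6–17% |

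Per 20-man arm, placebo included, the six-visit range is 20 × 0.17 = 3.4 to 20 × 0.69 = 13.8 men. With one value it is 20 × 0.06 = 1.2 to 20 × 0.23 = 4.6 men.

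*2. Common drift.* Suppose all arms shift by δ SD and there is no drug effect. The change in one man has SD √(2(1 − ρ)), so a paired t-test in one arm has noncentrality δ√18 / √(2(1 − ρ)).

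| δ | ρ | Noncentrality | P(within-arm p < 0.05) |
|---|---|---|---|
| 0.2 | 0.5 | 0.85 | 0.126 |
| 0.2 | 0.8 | 1.34 | 0.245 |
| 0.5 | 0.5 | 2.12 | 0.516 |
| 0.5 | 0.8 | 3.35 | 0.885 |

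Section 14.3 names no test, so these probabilities only illustrate how easily shared drift looks like an effect. In a comparison of change between arms, a common shift cancels. In simulation with screening selection, the between-arm test rejected 4.4–5.3% of the time against a nominal 5%.

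*3. Selection at screening.* Truncating screening values at the upper limit raises the later arm mean by only 0.01–0.10 SD (within-arm false-positive rate 5–7%). This covers limits with 2.5% to 10% of the population above them. Selection therefore matters for new threshold crossings and hardly at all for means.

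*4. What the arms can show.* With 18 per arm, two-sided 0.05 and 80% power, the detectable difference is (1.960 + 0.842) × √(2/18) = 0.93 SD. With baseline adjustment it is multiplied by √(1 − ρ²): 0.81 SD at ρ = 0.5 and 0.56 SD at ρ = 0.8. These comparisons are estimates, not powered tests.

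**The case against.** The strongest reply is that 14.3 is silent, not restrictive. It does not say that results will be pooled across arms, and nothing prevents tabulation by arm. The sentence "assessed and compared for each subject from screening to end of study" can also be read as individual safety review. This stands in part. A reader might infer that the plan rules out a placebo comparison, or that drug effects can never be separated in this trial. The documents do not support that: every arm has the same visits and measurements, so the limit lies in the written analysis and not in the data.

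A reader might also infer that the side-effect objective has no comparison at all. It has one: adverse-event incidence is examined by dose.

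Third, selection for normal chemistry is only partial. Exclusion 9 is firm for liver and kidney tests; lipids and other values depend on the investigator's judgment. This also stands, and step 3 shows that the argument does not need selection to shift means.

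Fourth, no passage defines a rule of any test high at any visit, and the result moves a good deal with the correlation between tests and the number of visits. Correct; hence the range.

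Finally, tabulating everything has a cost. Fifteen tests plus vital signs, weight and PHQ-9 make about 20 variables. At six visits and two doses that is 20 × 6 × 2 = 240 intervals, of which about 240 × 0.05 = 12 would exclude zero by chance.

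None of this supplies the missing contrast. Section 14.3 specifies a by-dose view for adverse events and a within-man view for the rest, and no other section adds placebo.

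**Conclusion.** The point holds for the analysis as written. Laboratory, vital-sign and examination data are analysed as change within each man, PHQ-9 has no analysis in 14.3, and the randomized comparison is not used for any of them. With no drug effect, roughly 17–69% of men would show a new high value over six visits, or 6–23% with one post-screening value. These ranges rest on the stated assumptions (8 to 12 tests, 97.5% limit, within-man correlation 0.5 to 0.85, between-test correlation 0 to 0.5) and not on trial data.

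A reader might take the upper end, about 14 of 20 placebo men, as the expected count. It is not: it needs twelve independent tests, six visits and the lowest within-man correlation together.

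This is a cheap improvement to a descriptive safety summary in a 60-man pilot. The primary endpoint is unaffected.

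**What to change.** In section 14.3:

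- For each laboratory test, each vital sign and the PHQ-9 total, summarise change from baseline by arm. Give the difference of each dose from placebo with a 95% CI at week 24, and show other visits descriptively. With about 20 variables this is 20 × 2 = 40 intervals instead of 240, with about 40 × 0.05 = 2 expected to exclude zero by chance.
- Give counts, by arm, of men newly outside the normal range, and of men with new examination findings.
- State which value is baseline. Section 14.3 refers to screening, while Appendix 1 also marks chemistry at day 0.
- Reconcile the chemistry schedule. The synopsis gives screening and end of treatment; section 12.4.2 and Appendix 1 give every treatment visit. The number of post-baseline values depends on it.
- Label the intervals as unadjusted descriptive estimates, not tests.

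The cost is more tables and many imprecise intervals. With 18 evaluable men per arm, the half-width is about 1.96 × √(2/18) = 0.65 SD, or 0.39–0.57 SD with baseline adjustment (ρ = 0.8 to 0.5). The by-arm analysis itself needs no extra men, visits or samples.

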16.1 Informed Consent

Principal investigators will provide the NICHD with a copy of the Informed Consent approved by their local Institutional Review Board (IRB). The appended Informed Consent (Appendix 2 and Appendix 3) will be translated and certified into the language of the respondent as needed.

Under this consent, the subject shall understand that he is authorizing access to medical records as required for monitors, auditors, IRBs and regulatory authorities. To expedite collection of supporting documentation in the event of a serious adverse event, the subject should also be asked to provide a release of medical records authorization at the enrollment visit.

16.2 Conflicts of Interest

The investigators will not profit from results, either positive or negative, with regard to the product being evaluated.

16.3 Subject Recruitment

The subjects will be recruited from our Infertility and Urology clinics as well as from greater Seattle Metropolitan infertility clinics, who see >300 such men annually. The study coordinator will screen potential subjects over the phone by inquiring about their age and medical history. Potential subjects who qualify by phone screen will be scheduled for an appointment to consult with the investigator about further eligibility requirements for the study.

17. Confidentiality

The information on individual subjects arising from this study is to be considered confidential and transmitted to the sponsor only in a form that will not permit identification of the individual. Regulatory and sponsoring agencies may request access to the study records and related medical records of each participating subject, and if requested, the subject's identity will remain confidential to the extent permitted by the applicable laws and regulations. All records will be kept in a secure storage area with limited access.

18. **Investigative Record Management**

All investigative site records will be kept in a secure storage area with limited access. NICHD should be notified before destruction of any site records.

19. Data Transmission

Not applicable

20. Publication Policy

Data on the use of the study medication and results of all clinical and laboratory studies are considered private and confidential, and NICHD will encourage publication of the results of the study.

21. Investigator Documentation

Prior to beginning the study, the investigator will be asked to demonstrate compliance with ICH E6, 8.2 and 21 CFR 312 by providing the following essential documents, including but not limited to:

- 1. An original signed Investigator Agreement page of the protocol.
- 2. An original signed acknowledgement of receipt of the Investigator's Brochure.
- 3. An Institutional Review Board (IRB) -approved Informed Consent (as described in section 18.1) in the local language.
- 4. Local IRB approval.
- 5. Form FDA 1572, fully executed, and all updates on a new fully executed Form FDA 1572.
- 6. Current curriculum vitae (CV) for each principal investigator and each sub investigator listed on Form FDA 1572.
- 7. Financial disclosure information to attest to the absence of financial interests and arrangements, including any equity interests in the sponsor or proprietary interest in the tested product, which could introduce bias in the study conduct.

22. References

Appendix 1: Schedule of Events

		Scre	ening	Treatn	nent	Follow-up
	Visit Number	1	2	1	2-7	3
	Study Day	6	-30	0	Wk 4, 8, 12, 16, 20 and 24	Wk 28 and 36
Administ rative	Inform consent/HIPAA signed	X				
Clinical	Vital signs	X		X	X	X
	Medical history	X				
	Physical exam	X		X	X	X
	AE & ConMed	X		X	X	X
	Semen analysis	X	X	X	X	X
	PHQ9 questionnaire	X	X	X	X	X
Blood Sampling	CBC and Clinical Chemistry	X		X	X a	X
	FSH, LH, T, retinoids	X		X b	X b	X
Orug	Dispense study medication			X		
Administrat	Dispense study medication log			X		
on	Collect and review study medication log				X	
	Collect unused study medication				X	

a:

This blood collection requires fasting.

Sampling of blood will be collected every 15 minutes for one hour during which a total of five 30, 45 and 60 minutes) will be collected for this visit. samplings (0, 15,

Appendix 4: PHQ9 Questionnaire

PATIENT HEALTH QUESTIONNAIRE (PHQ-9)

NAME:		_ DATE:		
Over the last 2 weeks, how often have you been bothered by any of the following problems?				
(use "✓" to indicate your answer)	Not at all	Several days	More than half the days	Nearly every day
Little interest or pleasure in doing things	0	1	2	3
2. Feeling down, depressed, or hopeless	0	1	2	3
3. Trouble falling or staying asleep, or sleeping too much	0	1	2	3
4. Feeling tired or having little energy	0	1	2	3
5. Poor appetite or overeating	0	1	2	3
Feeling bad about yourself—or that you are a failure or have let yourself or your family down	0	1	2	3
Trouble concentrating on things, such as reading the newspaper or watching television	0	1	2	3
8. Moving or speaking so slowly that other people could have noticed. Or the opposite — being so figety or restless that you have been moving around a lot more than usual	0	1	2	3
Thoughts that you would be better off dead, or of hurting yourself	0	1	2	3
	add columns		+	+
(Healthcare professional: For interpretation of TOT) please refer to accompanying scoring card).	AL, TOTAL:			
10. If you checked off any problems, how difficult have these problems made it for you to do your work, take care of things at home, or get along with other people?		Somewl	cult at all hat difficult ficult ely difficult	

 $\label{eq:copyright} \ @\ 1999\ Pfizer\ Inc.\ All\ rights\ reserved.\ Reproduced\ with\ permission.\ PRIME-MD@\ is\ a\ trademark\ of\ Pfizer\ Inc.\ A2663B\ 10-04-2005$

Confidential

Appendix 5: Serious Adverse Event Report Form

SERIOUS ADVERSI	E EVENT REPO	RT	CBR	SERIAL NO:	•			
I. EVENT INFORMA	ATION							
1. PATIENT INITIALS	1.a COUNTR Y	2. DATE OF BIRTH Day Month Year		2.a. AG E	3. SE X	3.a. HEIGHT		3.b. WEIG HT
				year s				kg
7 13. DESCRIBE EVENT. UNEXPECTED		EXPECTED)				VENT ONS onth Year	ET
DIAGNOSIS: Description:						TO EVDEA Day Ye	RIA COPRIATE ENT ATH (DATE Month	
						DIS. INCAPLIFIOTF CRITE (Car anomal	ABILITY ACITY E-THREAT HER RIA ncer,	OR ENING SERIOUS congenital
II. SUSPECT DRUG	INFORMATION					NO	Γ APPLICA	BLE
14. SUSPECTED DRUG(S) (i							?	BATE TOPPING
15. DAILY DOSE (include scl	nedule)	16. ROUTE	OF ADM	INISTRATION		NO	Γ APPLICA	BLE

Confidential

17. INDICATION(S) FOR USE			21. DID EVENT RE-
			APPEAR AFTER REINTRODUCTION?
			REINTRODUCTION?
18. THERAPY DATES (from/to)		19. THERAPY DURATION UNTIL REACTION	YES
Day Month Year Day Month	Year	ONSET	NO
			NOT APPLICABLE
III. CONCOMITANT DRU	JGS AND HISTOR	Y	
22. CONCOMITANT DRUGS AND D	ATES OF ADMINISTRAT	TION (exclude those used to treat reaction)	
23. OTHER RELEVANT HISTORY (e	e.g. diseases, allergies, pregi	nancy etc.)	
IV.IND HOLDER INFORM	MATION	V. INVESTIGATOR'S AS	SSESSMENT
24.a. NAME AND ADDRESS OF IND	HOLDER	23.d. OUTCOME	23.e. CAUSALITY
Population Council			
Center for Biomedical Research		Pagayarad	Not Poloted
		Recovered	Not Related
[name]		Recovering	Unlikely
[name] [name]		Recovering Not Recovered	Unlikely Possible
		RecoveringNot RecoveredSequelae	Unlikely Possible Probable
[name]	24.b. PATII	Recovering Not Recovered Sequelae Fatal	Unlikely Possible Probable Highly Probable
[name] [contact]	24.b. PATII IDENTIFIER NO	RecoveringNot RecoveredSequelaeFatal	Unlikely Possible Probable
[name] [contact] BATCH NO. (when		Recovering Not Recovered Sequelae Fatal	 Unlikely Possible Probable Highly Probable Insufficient
[name] [contact] BATCH NO. (when		Recovering Not Recovered Sequelae Fatal	Unlikely Possible Probable Highly Probable Insufficient
[name] [contact] BATCH NO. (when		Recovering Not Recovered Sequelae Fatal Unknown	Unlikely Possible Probable Highly Probable Insufficient Data
[name] [contact] BATCH NO. (when relevant)	IDENTIFIER NO	Recovering Not Recovered Sequelae Fatal Unknown	Unlikely Possible Probable Highly Probable Insufficient Data
[name] [contact] BATCH NO. (when relevant)	IDENTIFIER NO	Recovering Not Recovered Sequelae Fatal Unknown	Unlikely Possible Probable Highly Probable Insufficient Data
[name] [contact] BATCH NO. (when relevant)	IDENTIFIER NO	Recovering Not Recovered Sequelae Fatal Unknown	Unlikely Possible Probable Highly Probable Insufficient Data
[name] [contact] BATCH NO. (when relevant) 24.c. DATE RECEIVED Day Month Year	IDENTIFIER NO 24.d. TRIAL NUMBER	Recovering Not Recovered Sequelae Fatal Unknown	Unlikely Possible Probable Highly Probable Insufficient Data
[name] [contact] BATCH NO. (when relevant) 24.c. DATE RECEIVED Day Month Year 24.e. DATE OF THIS	IDENTIFIER NO 24.d. TRIAL NUMBER	Recovering Not Recovered Sequelae Fatal Unknown	Unlikely Possible Probable Highly Probable Insufficient Data
[name] [contact] BATCH NO. (when relevant) 24.c. DATE RECEIVED Day Month Year 24.e. DATE OF THIS REPORT	24.d. TRIAL NUMBER 25.a. REPORT TYPE	Recovering Not Recovered Sequelae Fatal Unknown	Unlikely Possible Probable Highly Probable Insufficient Data

Add another page if not sufficient space. If this case is from literature, please attach an original article
